5.4.2 Analysis Visits for Endpoints Derived Based on Monthly Data Collection

Since the actual visit for a subject may not exactly coincide with their targeted visit date, the actual visit date is mapped to the analysis visit as in [Table 5-3](#), [Table 5-4](#), [Table 5-5](#), and [Table 5-6](#).

For by-visit summaries, if more than one visit with non-missing measurement (including the unscheduled visits, ie, CPEVENT = 'UNSCHED') fall within the same visit window, the following rules will be applied according to the order described below for selecting one visit per visit window for summary:

1. Scheduled visit will be used regardless of the distance from the target day.
Unscheduled visit will only be used when there is no measurement from scheduled visit in the visit window.
2. The visit closest to the target day among visits of the same type (all scheduled visits or all unscheduled visits) will be considered for analysis.
3. If two assessment dates are equidistant from the target date, the latter visit will be considered for analysis.

Table 5-3. MFIQ, MSSS, and MIBS-4 Analysis Visit Windows

Study Period	Analysis Visit	Target Day	Visit Window (Study Day)
Baseline Period	Day 1 (Baseline)	1	Last measurement ≤ Day 1
Open-label Treatment Period	Week 12 (Month 3)	85	72 to 99
	Week 16 (Month 4)	113	100 to 127
	Week 20 (Month 5)	141	128 to 155
	Week 24 (Month 6)	169	≥ 156

Table 5-4. mGI-I Analysis Visit Windows

Study Period	Analysis Visit	Target Day	Visit Window (Study Day)
Open-label Treatment Period	Week 12 (Month 3)	85	72 to 99
	Week 16 (Month 4)	113	100 to 127
	Week 20 (Month 5)	141	128 to 155
	Week 24 (Month 6)	169	≥ 156

Table 5-5. GAD-7 and PHQ-9 Analysis Visit Windows

Study Period	Analysis Visit	Target Day	Visit Window (Study Day)
Baseline Period	Day 1 (Baseline)	1	Last measurement ≤ Day 1
Open-label Treatment Period	Week 12 (Month 3)	85	72 to 99
	Week 24 (Month 6)	169	≥ 156

Table 5-6. TSQM Version 1.4 Analysis Visit Windows

Study Period	Analysis Visit	Target Day	Visit Window (Study Day)
Baseline Period	Day 1 (Baseline)	1	Last measurement ≤ Day 1
Open-label Treatment Period ^a	Week 12 (Month 3)	85	79 to 106
	Week 16 (Month 4)	113	107 to 134
	Week 20 (Month 5)	141	135 to 162
	Week 24 (Month 6)	169	≥ 163

^a The recall period for TSQM Version 1.4 is the last 2 to 3 weeks.

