8.1.2 Treatment Period

Visits will occur per the Schedule of Activities ([Table 1-1](#)). On-study visits may be completed within \pm 7 days. The date of the first dose of erenumab is defined as day 1.

All subsequent doses and study visits will be scheduled based on the day 1 date.

Erenumab is to be administered by site staff or by subject self-administration as the last procedure of the onsite visits. All other doses of erenumab are to be administered by subject or designee at a non-investigative site setting (eg, at home), unless a site visit is deemed warranted by the investigator (eg, for changes in erenumab dose).

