8.1.3 End of Study

The end of study visit occurs at week 24 (\pm 7 days) or when a subject discontinues from the study before the week 24 visit. All assessments will be performed at the end of study visit as per the Schedule of Activities ([Table 1-1](#)).

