5.3 Study Points of Reference

Baseline Assessment

Baseline assessment for the endpoint of the interest is defined as the last non-missing measurement taken or the monthly interval assessed (for endpoints derived from daily eDiary collection during baseline period) before the first dose of investigational product. In cases where baseline measurements are taken on the same day as IP, it will be assumed that these measurements are taken prior to IP being administered.

Study Day 1

Study Day 1 is defined as the first IP dose date **or enrollment date if no IP received**.

Study Day

Study Day is defined as the number of days from Study Day 1.

Before Study Day 1:

Study Day = (Date of Interest – Date of Study Day 1)

On or after Study Day 1:

Study Day = (Date of Interest – Date of Study Day 1) + 1

Therefore, the day prior to Study Day 1 is -1.

Treatment Discontinuation Visit

Treatment discontinuation visit is defined as the earliest visit on or after the date when the decision to discontinue treatment is made.

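### TSQM analysis windows open one day after the protocol's visit window, so a compliant day-162 week-24 visit is filed under week 20 and cannot supply the primary endpoint

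*SAP*

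**What the plan says.** The protocol fixes the visit calendar in Section 8.1.2. Day 1 is the anchor ("The date of the first dose of erenumab is defined as day 1"), later visits follow from it ("All subsequent doses and study visits will be scheduled based on the day 1 date"), and there is a tolerance: "On-study visits may be completed within \pm 7 days". Section 8.1.3 repeats the same tolerance for the final visit ("The end of study visit occurs at week 24").

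The SAP counts days from the same anchor in Section 5.3: "Study Day = (Date of Interest – Date of Study Day 1) + 1". Section 5.4.2 then assigns each assessment to an analysis visit from its actual date, not its nominal visit name. For the TSQM this is done in "Table 5-6. TSQM Version 1.4 Analysis Visit Windows", with target days 85, 113, 141 and 169 and windows 79 to 106, 107 to 134, 135 to 162, and 163 or later. A footnote gives the two-to-three-week recall period as background. The windows for MFIQ, MSSS, MIBS-4 and mGI-I (Tables 5-3 and 5-4) are 72 to 99, 100 to 127, 128 to 155, and 156 or later. GAD-7 and PHQ-9 (Table 5-5) use the same week-12 and week-24 windows.

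When two assessments share a window, a scheduled visit outranks an unscheduled one. After that, "The visit closest to the target day among visits of the same type (all scheduled visits or all unscheduled visits) will be considered for analysis".

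**The concern.** The tolerance runs from target minus 7, but the TSQM windows start at target minus 6. The first permitted day of every TSQM visit therefore falls outside that visit's own window. The day that matters most is 162, because week 24 is the timepoint for the primary endpoint (TSQM overall satisfaction) and for the Item 14 secondary endpoint. Week 24 is also the end-of-study visit, so no later scheduled TSQM could fill the window that opens at day 163.

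A subject who attended on schedule would be treated as having no week-24 satisfaction score, while the MFIQ and mGI-I completed at the same visit would be analysed as week 24. One visit would carry two labels within one set of results.

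**Working it through.** **Inputs.** Visit tolerance of 7 days either side (Protocol 8.1.2, 8.1.3); study-day formula (SAP 5.3); TSQM windows (SAP Table 5-6); windows for the other questionnaires (SAP Tables 5-3 to 5-5); effective sample size 216 = 240 × 0.9 (SAP 3.2).

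**Step 1: reproduce the target days.** Target = 7 × week + 1. Weeks 12, 16, 20 and 24 give 85, 113, 141 and 169, exactly as in Table 5-6.

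**Step 2: map every permitted day.**

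| Visit | Permitted days (target ± 7) | TSQM window | Permitted day misfiled | Where it goes |
|---|---|---|---|---|
| Week 12 | 78–92 | 79–106 | 78 | no visit |
| Week 16 | 106–120 | 107–134 | 106 | week 12 |
| Week 20 | 134–148 | 135–162 | 134 | week 16 |
| Week 24 | 162–176 | ≥ 163 | 162 | week 20 |

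The same mapping through Tables 5-3 to 5-5 misfiles no permitted day.

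**Step 3: apply the selection rules to a day-162 visit.** Its distance from the week-20 target is 162 − 141 = 21 days. A week-20 visit on days 135 to 148 is at most 7 days from that target. Both visits are scheduled, so the nearer one is kept and the day-162 value is dropped. This covers 14 of the 15 permitted week-20 days. If the week-20 visit was on day 134 (itself filed under week 16) or was missed, the day-162 value is kept but labelled week 20. In neither case does it count at week 24.

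**Step 4: size.** The documents give no distribution of visit days, so the share attending on day 162 is an assumption. The Item 14 half-width at 50% is 1.96 × √(0.25/n). With n = 216 it is 6.67%, which agrees with the 6.7% in SAP Table 3-2.

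| Assumed share on day 162 | Subjects losing week 24 | Half-width at 50% |
|---|---|---|
| 1% | 216 × 0.01 = 2.2 | 6.70% |
| 3% | 216 × 0.03 = 6.5 | 6.77% |
| 1/15 (uniform over the window) | 216/15 = 14.4 | 6.90% |
| 10% | 216 × 0.10 = 21.6 | 7.03% |

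These half-widths are for a simple proportion, not the planned mixed model.

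**The case against.** The strongest reply is that the windows are deliberate. Each TSQM window opens 22 days after the previous four-weekly target (57 + 22 = 79, 85 + 22 = 107, 113 + 22 = 135, 141 + 22 = 163), that is, once a full 21-day recall has passed. This fits all four rows and the footnote, although the SAP does not state the derivation. It could explain why the windows open later than day 156. It does not support filing day 162 under week 20: 162 − 21 = 141, so even a three-week recall reaches back no further than the week-20 target day. Nor could a fixed day 163 guarantee separation, because a permitted week-20 visit on day 148 is only 15 days before it.

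A second reply is that the selection rules are introduced for by-visit summaries, so their use in the model is an inference. That is fair. However, the date-to-visit mapping carries no such limit, the model has a visit term, and the SAP offers no other assignment. Even without the selection rule, day 162 is not week 24.

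Three further points stand. The value is strictly discarded only when a week-20 TSQM on days 135 to 148 shares the window; otherwise it is relabelled. The misfilings at weeks 12, 16 and 20 touch exploratory timepoints and reach the primary estimate only through the repeated-measures model. A uniform spread of visits is unlikely when sites aim for the target day. Against that, target minus 7 falls on the same weekday as the target, so a visit brought forward by exactly one week lands on it, and a subject consistently one week early would have all four TSQM assessments misfiled.

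**Conclusion.** The point holds. Table 5-6 conflicts with the protocol's visit tolerance by one day at each of four visits, and a compliant day-162 TSQM can never serve as the week-24 value. The mapping follows from the documents' own figures and needs no assumption; the number of subjects does. The effect is probably at the low end, a handful of subjects out of 216. The repeated-measures model still uses their other visits, so the primary estimate should move little, and there is no evidence of bias in a particular direction. It should still be corrected, because it loses or mislabels on-schedule data for the primary endpoint and gives one visit different labels across questionnaires.

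**What to change.** Open each TSQM window in Table 5-6 at target minus 7:

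- week 12: days 78 to 105
- week 16: days 106 to 133
- week 20: days 134 to 161
- week 24: day 162 or later

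The bounded windows remain contiguous and 28 days long, the start stays later than the day 156 used for the other questionnaires, and re-mapping all permitted days gives no mismatch. One sentence should also confirm that the same visit assignment and selection rules apply to the mixed models as well as to the by-visit summaries.

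The cost is four table rows and the matching programming. The only visits that change label are those on days 78, 106, 134 and 162. A visit running 21 days late would move to the next analysis visit, but it would already be outside the protocol's tolerance. The change should be made before database lock, since altering visit assignment for the primary endpoint afterwards would be open to challenge.

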5.4.3 Subject Disposition

Exposed to Investigational Product

Subjects are defined as exposed if they receive at least one dose of investigational product.

Completing the Investigational Product

Subjects are defined as completing investigational product if the primary reason for ending IP on End of IP eCRF is “Completed”.

Completing Study

Subjects are defined as completing study if they complete the entire 24 weeks of study evaluation. It will be derived from the End of Study eCRF with “Completed” as the primary reason for ending study.

On-study

Subjects are considered on-study if they **are enrolled and** have not yet completed their EOS visit.

5.5 Arithmetic Calculations

Duration of IP Exposure (Days)

Minimum (Last Dose Date + 27, EOS Date) – First Dose Date + 1

Change From Baseline

Postbaseline monthly value – Baseline, as defined in Section 5.4. If the baseline or postbaseline value is missing, the change from baseline value will be set to missing.

Percent Change From Baseline

The change from baseline divided by baseline and multiplied by 100:

$$\text{Percent Change From Baseline} = \frac{(\text{Postbaseline} - \text{Baseline})}{\text{Baseline}} \times 100$$

If the baseline value is 0 and the postbaseline value is also 0, the percent change from baseline is set to 0. If the baseline value is 0 and the postbaseline value is non-zero, the percent change from baseline is set to missing.

Mean Monthly Change From Baseline Over Multiple Months

Arithmetic Mean monthly change from baseline is the arithmetic mean of the observed monthly change from baseline values for the months with non-missing change from baseline values.

5.6 Disease Characteristics

Treatment Failure of Prior Migraine Preventive Medications

Treatment failure of prior migraine preventive medications is determined by the medications marked as “Prior Migraine Prophylactic” with “Reason for Stopping” being “Lack of Efficacy” or “Adverse reaction” or “Intolerance” on the Prior Migraine Prophylactic And Ongoing Migraine Prophylactic eCRF.

6. Analysis Sets

The following analysis sets are defined for this study.

6.1 Full Analysis Set

The full analysis set (FAS) consists of all subjects enrolled in the study. Analysis of disposition, demographic and baseline characteristics, important protocol deviations, and protocol deviations related to COVID-19 control measures will utilize the FAS.

6.2 Efficacy Analysis Set

The efficacy analysis set consists of a subset of subjects from FAS who receive at least 1 dose of investigational product. Analysis of efficacy endpoints will utilize the efficacy analysis set.

6.3 Safety Analysis Set

The safety analysis set (SAS) will consist of a subset of subjects from FAS who received at least 1 dose of investigational product. Analysis of safety endpoints and summary of investigational product administration will utilize the safety analysis set.

7. Planned Analyses

There is only one milestone analysis to be conducted for this study once **all the 240** enrolled subjects have completed the week 24/EOS visit. The data will be cleaned, and the database will be locked for the final analysis.

7.1 Final Analysis

The final analysis will be conducted when **all** enrolled subjects have completed the week 24/EOS visit.

8. Data Screening and Acceptance

8.1 General Principles

The objective of the data screening is to assess the quantity, quality, and statistical characteristics of the data relative to the requirements of the planned analyses.

8.2 Data Handling and Electronic Transfer of Data

The Amgen Global Study Operations-Data Management (GSO-DM) department will provide all data to be used in the planned analyses. This study will use the RAVE database. The electronic Clinical Outcome Assessments (eCOAs) data including eDiary, GAD-7, MFIQ, mGI-I, MIBS-4, MSSS, PHQ-9, TSQM version 1.4 questionnaires data will be stored outside of RAVE database. The database is subject to edit check outlined in the Data Management Plan (DMP).

8.3 Handling of Missing and Incomplete Data

Subjects may miss specific data points for a variety of causes. In general, data could be missing due to a subject's early withdrawal from study, a missed visit, inability to evaluate an endpoint at a particular point in time, and treatment discontinuation due to lack of efficacy, adverse event, or non-response. The efficacy endpoints will be collected via daily eDiary and monthly eCOA assessments device. Subjects could miss entering several days of daily migraine data or an eCOA assessment in each monthly interval.

The general procedures outlined below describe how missing data will be handled.

For the eDiary data collected daily, if at least 14 days of eDiary are collected in the monthly interval, then the monthly frequency measurements (eg, headache days, migraine days or acute migraine-specific medications days [AMSMD]) will be prorated based on the number of days with available information. If less than 14 days of eDiary are collected in the monthly interval, then the monthly frequency measurements will be set to missing ([Table 8-1](#)). For the descriptive summary of the mean monthly value calculated using the monthly value from each of months 4, 5, and 6, if a subject has at least one monthly value at months 4, 5, and 6, then the subject contributes to the summary statistics.

For the endpoints derived from the daily diary data, please refer to proration approach specified in [Section 5.1.1](#). On handling missing daily diary data. Missing monthly measurement after proration will be handled by statistical analysis approaches listed in [Section 9.5](#).

Table 8-1. Handling of Missing and Incomplete eDiary Data

Monthly Frequency Endpoint	Condition	Proration Method (Without Rounding)
Monthly frequency measurements (migraine days and acute migraine-specific medication days)	
A diary day is a day with all headache-related questions completed in eDiary.
 
If diary days in baseline or each post-baseline interval ≥ 14, apply proration for that monthly interval;
 
Else monthly frequency measurement is set to missing
	
Number of event days of interest in a monthly interval* 28/ Number of diary days in the monthly interval
 
Note: Event days of interest is referred to migraine days and acute migraine-specific medication days

Missing or incomplete dates will be listed as reported, except for incomplete start date of an adverse event or concomitant medication ([Table 8-2](#)).

Table 8-2. Imputation for Incomplete Start Date of an Adverse Event or Concomitant Medication

Missing	Imputation	Exception on Adverse Event Start Date
Day	01	Default to study day 1 if an adverse event started the same year and month as study day 1 and the flag indicates that the adverse event started on or after the first dose of investigational product on the Events eCRF
Day/Month	01 Jan	Default to study day 1 if an adverse event started the same year as study day 1 and the flag indicates that the adverse event started on or after the first dose of investigational product on the Events eCRF
Day/Month/Year	None	—

eCRF = electronic case report form

Missing data will not be imputed for safety endpoints.

8.4 Detection of Bias

The below mentioned factors that may bias the results of the study:

- Important protocol deviations likely to impact the analysis and interpretation of the efficacy endpoints
- Investigational product dosing non-compliance
- The timing of and reasons for early withdrawal from study treatment and from study

The incidence of these factors may be assessed. Important protocol deviations will be listed and/or tabulated in the clinical study report (CSR). If necessary, the incidence of other factors will be tabulated.

The reasons for early withdrawal from study treatment and from study will be tabulated and/or listed.

8.5 Outliers

Histograms will be examined to identify outliers in any of the continuous variables used in the analyses. Unexpected and/or unexplained values in categorical data will be identified by utilizing frequency tables.

Outliers will be queried by the study team before final database lock. The validity of any questionable values or outliers will be confirmed. Outliers or any questionable values with confirmed validity will be included in the analyses presented in this statistical analysis plan unless there is sufficient justification to exclude them. However, ad-hoc sensitivity analyses may be conducted to evaluate the influence of extreme values in the data.

8.6 Distributional Characteristics

Continuous endpoints of change from baseline value will be analyzed under normality assumption.

8.7 Validation of Statistical Analyses

Programs will be developed and maintained, and output will be verified in accordance with current risk-based quality control procedures.

Tables, figures, and listings will be produced with validated standard macro programs where standard macros can produce the specified outputs.

The production environment for statistical analyses consists of Amgen-supported versions of statistical analysis software; for example, the SAS System version 9.4 or later.

9. Statistical Methods of Analysis

9.1 General Considerations

Summary statistics will be computed at each timepoint of interest. For continuous endpoints, the following descriptive statistics will be computed: number of observations, means, standard deviations, standard errors, medians, first and third quartiles, minimums and maximums. For categorical endpoints, the summaries will contain the number and percentage of subjects in each category.

Due to lack of a control arm, all analyses should be considered as descriptive in nature. If a subject discontinued treatment due to lack of efficacy or adverse event, data on primary and secondary efficacy endpoints collected after treatment discontinuation will be defined based on the worst post-baseline value observed (for continuous endpoints) up to IP discontinuation (inclusive) or non-response (for binary endpoints) using a composite strategy. If a subject discontinued treatment due to other reasons, data collected after treatment discontinuation visit will be censored based on a hypothetical strategy and not be used in efficacy analyses as described in [Section 9.5](#).

Analysis for primary and secondary endpoints will be using observed data with intercurrent event handling; analysis for exploratory endpoints will be using observed data without intercurrent event handling. A sensitivity analysis using observed data without any intercurrent event handling will also be performed for primary endpoint.

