9.4.2 Methods of Analyses

9.4.2.1 General Considerations

Summary statistics will be computed at each timepoint of interest. For continuous endpoints, the following descriptive statistics will be computed: number of observations, means, standard deviations, standard errors, medians, first and third quartiles, minimums and maximums. For categorical endpoints, the summaries will contain the number and percentage of subjects in each category.

Due to lack of a control arm, all analyses should be considered as descriptive in nature. Data on any endpoints collected after treatment discontinuation due to lack of efficacy or adverse event will be defined based on the worst observed value (for continuous endpoints) or non-response (for binary endpoints) using a composite strategy. Data collected after treatment discontinuation due to other reasons will be censored based on a hypothetical strategy and not be used in efficacy analyses as described in [Section 9.4.2.2](#).

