9.4.2.2 Efficacy Analyses

Endpoint/ Estimand	Statistical Analysis Methods
Primary	
In the event of IP discontinuation due to lack of efficacy or adverse event, the TSQM overall satisfaction scale score after treatment discontinuation will be defined as the worst postbaseline value observed up to IP discontinuation (inclusive). Any TSQM data collected after treatment discontinuation due to other reasons will be censored and not included in the analysis.
 
The primary endpoint will be analyzed using a repeated measures mixed effects model, including baseline TSQM overall satisfaction scale score, visit, the prevailing erenumab dose from week 12 onwards, and baseline MMD based on observed data. The mean change from baseline in TSQM overall satisfaction scale score at week 24 will be estimated from the least-squares mean (LSM) of the mixed effects model, and the corresponding 95% CI will be provided. The nominal p-value will be reported by comparing the mean change from baseline in TSQM overall satisfaction scale score at week 24 to zero with a two-sided 5% significance level.

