Secondary	
In the event of IP discontinuation due to lack of efficacy or adverse event, the binary secondary endpoint after IP discontinuation will be classified as not achieving overall satisfaction or global impression on improvement; and the continuous MFIQ domain scores after treatment discontinuation will be defined as the worst postbaseline value observed before treatment discontinuation. Data collected after IP discontinuation due to other reasons will be censored and not included in the analysis.
 
A generalized linear mixed effects model with the appropriate link function will be used to analyze each secondary endpoint based on observed data. The model will include the corresponding baseline value for the endpoint being analyzed (except for the global impression endpoints), visit, the prevailing erenumab dose from week 12 onwards, and baseline MMD.
 
For binary secondary endpoints, logit link function will be used, and the proportions and the corresponding 95% CI at week 24 will be estimated from the LSM (with inverse link function) of the mixed effects model.
 
For the continuous MFIQ domain score endpoints, identity link function will be used, and mean change from baseline in each domain score at week 24 with the corresponding 95% CI will be estimated from the LSM of the mixed effects model, and p-values comparing with zero at a 2-sided 5% significance level will be reported.

Exploratory	Will be described in the statistical analysis plan (SAP) finalized before database lock

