2.1 Objectives and Endpoints/Estimands

Objectives	Endpoints
Primary	

 To evaluate the effect of erenumab on medication-specific treatment satisfaction 	
 Change from baseline in the Treatment Satisfaction Questionnaire for Medication (TSQM) overall satisfaction scale score at week 24, as measured by items 12 to 14 of the TSQM version 1.4
Primary Estimand	

The estimand for the primary efficacy objective consists of:
 
 The target population, which includes subjects with Episodic Migraine (EM) or Chronic Migraine (CM) currently on 1 standard of care migraine prevention therapy The endpoint, which is the change from baseline in TSQM overall satisfaction scale score at week 24, as measured by items 12 to 14 of the TSQM There are 2 intercurrent events, discontinuation of investigational product (IP) due to lack of efficacy or adverse event, and discontinuation of IP due to other reasons. The treatment effect of interest will be assessed for all subjects who receive least 1 dose of IP and have a baseline score and at least 1 post-baseline score on the TSQM overall satisfaction scale. A composite strategy will be used for subjects who discontinued IP due to lack of efficacy or adverse event with data after IP discontinuation, defined by the worst postbaseline 	

value observed up to IP discontinuation (inclusive). A hypothetical strategy will be used for those subjects who discontinued IP due to other reasons with data collected after IP discontinuation censored.

- The treatment, which is erenumab 70 or 140 mg every 4 weeks
- The summary measure, which is the mean change from baseline in TSQM overall satisfaction scale score at week 24, as measured by items 12 to 14 of the TSQM

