The primary estimand for the primary efficacy objective is the mean change from baseline in TSQM overall satisfaction scale score at week 24 in subjects with EM or CM who are currently on 1 standard of care migraine prevention therapy and who receive at least 1 dose of IP and have a baseline and at least 1 post-baseline TSQM overall satisfaction scale score, and a composite strategy will be used for subjects who discontinued IP due to lack of efficacy or adverse event with data after IP discontinuation defined by the worst postbaseline value observed up to IP discontinuation (inclusive), while a hypothetical strategy will be used for those subjects who discontinued IP due to other reasons with data collected after IP discontinuation censored.

Secondary

• To assess the effect of erenumab on medication-specific treatment satisfaction	
• Achievement of overall satisfaction at week 24 as defined by subject reporting of satisfied, very satisfied, or extremely satisfied on Item 14 of the TSQM version 1.4
--	--

The estimand for the secondary efficacy objective on treatment satisfaction consists of:

- The target population, which includes subjects with EM or CM currently on 1 standard of care migraine prevention therapy
- The endpoint, which is achievement of overall satisfaction at week 24 as defined by subject reporting of satisfied, very satisfied, or extremely satisfied on Item 14 of the TSQM

- There are 2 intercurrent events, discontinuation of IP due to lack of efficacy or adverse event, and discontinuation of IP due to other reasons. The treatment effect of interest will be assessed for all subjects who receive at least 1 dose of IP and have a baseline value and at least 1 post-baseline value for Item 14 of the TSQM. A composite strategy will be used for subjects who discontinued IP due to lack of efficacy or adverse event where they will be defined as not satisfied after IP discontinuation. A hypothetical strategy will be used for those subjects who discontinued IP due to other reasons with data collected after IP discontinuation censored.
- The treatment, which is erenumab 70 or 140 mg every 4 weeks
- The summary measure, which is the proportion of subjects who achieves overall satisfaction at week 24

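### SAP 9.1 limits the composite rule to collected data, but the binary secondary estimands have no such limit, so some subjects defined as failures can be missing at week 24

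*SAP*

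**What the plan says.** Two places tie the composite rule to data that exist. SAP 9.1 says that "data on primary and secondary efficacy endpoints collected after treatment discontinuation will be defined based on the worst post-baseline value observed (for continuous endpoints", with non-response for binary endpoints, and adds: "Analysis for primary and secondary endpoints will be using observed data with intercurrent event handling". Protocol 9.4.2.1 has the same limit: "Data on any endpoints collected after treatment discontinuation due to lack of efficacy or adverse event will be defined".

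Other places do not. For binary endpoints, protocol 9.4.2.2 states that "the binary secondary endpoint after IP discontinuation will be classified as not achieving overall satisfaction or global impression on improvement". SAP 2.1 says of TSQM item 14 that "they will be defined as not satisfied after IP discontinuation", and it treats the three mGI-I endpoints in the same way (not improved).

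The continuous endpoints are less clear. Protocol 9.4.2.2 says that the TSQM score after stopping "will be defined as the worst postbaseline value observed up to IP discontinuation (inclusive". The primary estimand in SAP 2.1 speaks of subjects who stopped "due to lack of efficacy or adverse event with data after IP discontinuation". That phrase can restrict the rule to subjects with later data, or it can simply introduce the value that such data take.

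SAP 8.3 lists among the causes of missing data "and treatment discontinuation due to lack of efficacy, adverse event, or non-response". Its handling rules cover diary days and incomplete dates, not missed questionnaires.

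**The concern.** The plan separates two intercurrent events. Stopping for lack of efficacy or an adverse event gets a composite strategy. Stopping for other reasons gets a hypothetical one, with later data censored. Under the literal SAP 9.1 rule the distinction disappears for anyone who leaves the study: both kinds of stopper are missing at week 24, and the mixed model treats both as ignorable. A subject whom the binary estimand defines as a failure is then given a positive predicted chance of success. With no comparator arm, nothing offsets the upward shift. Two programmers, one following SAP 9.1 and one following SAP 2.1, could report different week-24 proportions.

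A second, narrower gap concerns the TSQM overall score and the MFIQ domains, which are first scheduled after baseline at week 12. A subject who stops for these reasons before any post-baseline score, stays on study and scores later has no worst value from which the rule can work.

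**Working it through.** **Does another rule fill the missing week-24 value?**
- Protocol 8.1.3 gives early leavers an end-of-study visit, but SAP 5.4.2 maps visits by study day. It counts as week 24 only from day 156 (mGI-I, Table 5-4) or day 163 (TSQM, Table 5-6). An earlier one can record failure only at an earlier visit.
- The sensitivity analysis in SAP 9.1 covers only the primary endpoint and removes intercurrent-event handling.
- SAP section 10 does not list the SAP 9.1 wording as a change from the protocol.

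So nothing fills it.

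**Plan figures.** SAP 3.2: 240 enrolled, 10% dropout, 240 × 0.9 = 216 effective, 24 assumed dropouts from all causes. The half-width at 70% is 1.96 × √(0.7 × 0.3 / 216) = 6.1%, as in Table 3-2.

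**Size for a binary endpoint.** Let k subjects have a week-12 response, stop for these reasons and leave. Let q be their predicted chance of success at week 24. The literal rule gives (216 × 0.70 + kq)/(216 + k) and the estimand gives (216 × 0.70)/(216 + k). The overstatement is q × k/(216 + k).

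Assumptions: a latent normal response with 70% success at each visit and equal correlation r between visits, r = 0.5 or 0.8. Let A be the joint probability of success at two visits and B at three. For r = 0.5, A = 0.5568 and B = 0.4696. For r = 0.8, A = 0.6112 and B = 0.5613. Results below use unrounded values.

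With k = 6 the weight is 6/222 = 0.0270; with k = 12 it is 12/228 = 0.0526.

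| Recorded history | Formula for q | q (r = 0.5 / 0.8) | k = 6, points | k = 12, points |
|---|---|---|---|---|
| Week 12 not satisfied | (0.70 − A)/0.30 | 0.477 / 0.296 | 1.3 / 0.8 | 2.5 / 1.6 |
| Week 12 satisfied | A/0.70 | 0.795 / 0.873 | 2.1 / 2.4 | 4.2 / 4.6 |
| Not satisfied, then failure at a later visit | (0.70 − 2A + B)/(1 − 1.40 + A) | 0.357 / 0.185 | 1.0 / 0.5 | 1.9 / 1.0 |
| Satisfied, then failure at a later visit | (A − B)/(0.70 − A) | 0.609 / 0.561 | 1.6 / 1.5 | 3.2 / 3.0 |

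This approximates the effect on a population proportion. It is not a fit of the planned model.

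**Size for a score, if read literally.** The shift is (1 − r) × d × k/(216 + k), where d is the assumed shortfall of the subject's worst score below the mean of those continuing. With d = 10, k = 6, r = 0.8: 0.2 × 10 × 6/222 = 0.05 points. With d = 20, k = 12, r = 0.5: 0.5 × 20 × 12/228 = 0.5 points.

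**The case against.** Read as a whole, the SAP arguably answers the question. Section 9.1 is a general section that names a composite strategy, section 2.1 defines that strategy for the binary endpoints without any limit, and Table 9-2 uses data after intercurrent-event handling. This shows which reading was probably meant. It does not remove a rule in the analysis section that says otherwise.

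Protocol 9.4.2.2 also models observed data and never says that a missed questionnaire receives a value. That stands for the TSQM overall score and MFIQ. A reader might infer that the primary endpoint has two clearly opposed rules, but the documents show only shared silence about uncollected scores.

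A reader might also take all 24 assumed dropouts as affected, which would shift a 70% proportion by as much as 8.7 points (0.873 × 24/240), more than the half-width. The documents do not support that. Every dropout would have to stop for one of these two reasons, answer at week 12 and leave with no later response. Protocol 7.1 urges retention and lists subject request and loss to follow-up as separate reasons for ending treatment. Neither lack of efficacy nor an adverse event is a reason for leaving the study in protocol 7.2.2. Even at 24, one later recorded failure lowers the satisfied-at-week-12 case to 5.6–6.1 points and the not-satisfied case to 1.8–3.6.

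Finally, the study is descriptive with no hypothesis, and SAP 9.2 tabulates reasons for discontinuation. That limits the harm but does not correct the estimates.

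**Conclusion.** For TSQM item 14 and the three mGI-I endpoints the conflict is real: SAP 9.1 and protocol 9.4.2.1 on one side, protocol 9.4.2.2 and SAP 2.1 on the other. Followed literally, SAP 9.1 overstates the week-24 proportion relative to the stated estimand. The direction is certain whenever such a subject exists; the size is not, because the number affected is unknown. With 6 to 12 leavers who have only a week-12 response, the illustration gives about 0.8–2.5 points if they were not satisfied then and 2.1–4.6 if they were. With one later recorded failure it gives 0.5–1.9 or 1.5–3.2. These figures rest on the assumed 70% proportion, correlations and counts.

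For the TSQM overall score and MFIQ the finding is ambiguity plus a missing definition for a narrow group. The literal reading favours erenumab there only if the subject's worst score is poorer than the average of those continuing, which is likely but not certain.

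**What to change.** - **Binary endpoints.** Amend SAP 9.1 and protocol 9.4.2.1 to match protocol 9.4.2.2 and SAP 2.1. A subject who meets the estimand's condition and stops for lack of efficacy or an adverse event is a non-responder at every scheduled analysis visit after stopping, through week 24, whether or not that visit's questionnaire was completed.
- **Keep the condition in the rule.** It is at least one dose and at least one post-baseline value for that endpoint and respondent, plus a baseline value for TSQM item 14. The efficacy analysis set in SAP 6.2 requires only a dose, so without the condition the rule would count as failures subjects who never responded. It would do the same for those with no participating family member (protocol 4.1 invites one only if available), while comparable continuing subjects stay missing.
- **TSQM and MFIQ scores.** Apply the worst post-baseline value in the same way. State whether the inclusive cut-off means the treatment discontinuation visit of SAP 5.3; SAP 9.1 uses that term only for censoring. If it does, a week-12 score could serve a subject who stops after the week-8 visit, but the gap remains for earlier stoppers. Pre-specify a fallback when no value exists, with one alternative as a sensitivity analysis. Zero change is not a neutral fallback for TSQM, because protocol Table 1-1 has the day 1 questionnaire rate the standard-of-care drug. Align the MFIQ wording in protocol 9.4.2.2, which says before discontinuation, with the inclusive wording elsewhere.
- **Reporting.** Give the number of subjects assigned a composite value and the number assigned the fallback.

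The cost is wording in both documents, one derivation step (the End of IP eCRF already holds the reason for stopping), one extra table, and a slightly less favourable estimate.
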